The first intervention is a randomized controlled trial focused on patients. This intervention is broken into two separate but identical parts, in which half of the patient sample participates before the physician intervention, and the other half participates after the physician intervention. In the first part, patients of participating physicians will be recruited and tracked until they become eligible for a trial, at which time they will be randomized into an intervention or usual care group. They will continue their participation until: they receive a trial offer, or they have four interactions with their physician without receiving an offer. Regardless of the number of interactions, this group of patients will discontinue their active participation when the physician intervention begins. Thus, these patients will participate for a maximum of 20 months. In the second part, which occurs after the physician intervention has been conducted, the remaining half of the patient sample will be recruited and tracked, and eligible patients will be randomly assigned to the two groups. Again, their participation will continue until they receive a trial offer, they have four interactions with their physician without an offer, or data collection ends. These patients will, thus, also participate for a maximum of 20 months. We will utilize a block-randomized design in which physicians are treated as blocks and patients are randomized to a group.

The second intervention is a within-subjects interrupted time series quasi-experiment focused on physicians.³⁰ Physicians will be recruited at the beginning of data collection, prior to any patient recruitment (i.e., once IRB approval has been received—approximately nine months after the formal start date of this grant award). In this within-subjects design, physicians provide pre-intervention data for 20 months, then receive the intervention and continue their participation for another 20 months (i.e., until the end of data collection). The same physicians will remain in the study throughout data collection; thus they will provide both pre intervention and post intervention data that will be used to examine the effectiveness of the physician-focused intervention.

Figure 2: Study Design and Procedures Overview

Patient Procedures, Measures, and Intervention

Patient Procedures.

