Power and Sample Size Estimates. A within-subject design is used to evaluate the physician intervention and a randomized control trial is used to evaluate the patient intervention. However, the outcomes of both interventions will be modeled at the patient level in a single model. We used the person-level multi-site/block trial design within Optimal Design to conduct power analyses because the unit of analysis is the patient-physician visit and data from these visits will likely be more similar within physicians than between physicians. The first power analysis is based 216 patients not lost to attrition, who should be eligible for clinical trials and thus randomized into the patient-level intervention. (See Participants and Recruitment—p. 7) We define the *primary outcome* of our study as patients' decisions to enroll in clinical trials, where a "success" is defined as a patient deciding to enroll. Our primary objective (Aim 1) is to examine the extent to which patient- and physician-level interventions affect physician and patient trial-related decisions, and thus we seek a sample size that gives us sufficient power to detect both the main effect of intervention and important interaction effects. We chose GEE power analysis for nested binomial outcomes with within-cluster treatments⁶⁶ as the best available model to estimate power for our primary objective; such estimates are lacking for HLM models. With 24 physicians and 9 patients per physician (i.e., 216 patients), a Type I error rate (α) of .05, and ICC of .05, and probability of success under the null hypotheses (p_{H_0}) of .25, we are well powered to detect p_H of .35 ($b = 0.48$, odds-ratio = 1.61) with power > .99. Our secondary objective, (i.e., Aim 2) is to examine whether patient race influences the effectiveness of either patient- or physician-level interventions on our primary outcome, and we remain well

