powered to detect 2-way and 3-way interactions. We will also examine effects of the interventions, and between-race differences in effects of the interventions on other binary or continuous outcomes (e.g., trial offers, patients' perceptions of patient-centeredness, perceived involvement in care, trust in physician, etc.). The power analysis described above holds for the binary outcomes. For the continuous outcomes, we used block person-randomized trial module in Optimal Design⁶⁷ to estimate power. Considering each of the 24 physicians as "blocks" and assuming about 9 patients per physician, a Type I error rate (α) of .05, between-physicians variability in effect size (σ_{β}^2) of .05, 5% of variance in outcomes due to physicians and a medium effect size (d) of .50, power to find effects exceeds .90. Our final objective, (Aim 3) is to explore the extent to which patient-physician communication mediates the effects of the interventions on the outcomes. We will use Multi-level Structural Equation Modeling (MSEM) that control for patient-physician nesting to fit path analyses. The specific structure (i.e. direct and indirect paths of the models) will be guided by results from analyses conducted for our first and second aims. We therefore consider the MSEM exploratory in that we are the first researchers to examine these effects in this context. Thus, at this point we lack the specification of the model parameters needed to provide accurate estimates of power for this exploratory aim.

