Control variables: At the patient level of the model, we will control for factors such as decisional control preferences, relevant attitudes, health literacy, number of boosters received, disease severity, co-morbidities, whether there is an available clinical trial for the patient, and if so, characteristics of the trial (e.g., difficulty, complexity). At the physician level, we will control for relevant racial and professional attitudes, and decisional control preferences. Because the physician-focused phase involves a quasi-experimental design, we will also control factors that might threaten the internal validity of the intervention, such as time since study has begun, and number of previous interactions between patients and physicians.

Hypothesis 1a. Outcomes will be significantly improved in the patient intervention group, relative to the usual care group. To test hypothesis 1a, we will fit separate MLMs to examine continuous and binary outcomes assessed during or after each visit in which a trial was discussed. The focal independent variable will be the dummy-coded variable indicating whether the patient was in the usual care or intervention group. Support for hypothesis 1a will be indicated by a significant coefficient for this independent variable (i.e. intervention/usual care).

Hypothesis 1b. Outcomes will be significantly improved for patients after the physician intervention, as compared to outcomes before the physician intervention. The focal independent variable is the dummy-coded variable indicating whether or not the patient's physician has received the physician intervention at the time of the clinic visit. Note that this variable is a within-subject variable among the physicians; however, because we theorize that the patient-physician communication quality is central to offers and acceptance of clinical trials, this variable is introduced in the model at level-1 (patients). Support for hypothesis 1b will be indicated by a significant physician-intervention coefficient (i.e., pre/post physician intervention).

Hypothesis 1c. The combined effects of the two interventions will be multiplicative, rather than simply additive. The focal independent variable is the dummy coded variable for the product interaction term in the model. We expect the physician intervention to be more effective among patients who received the patient intervention; we expect a statistically significant positive coefficient for the interaction term.

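### The stated power above .90 for continuous outcomes does not hold for the physician intervention (H1b), because the planned model adjusts for study time and the power calculation does not

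*Combined protocol and SAP*

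**What the plan says.** Power and Sample Size Estimates says that both interventions will be modelled at patient level in a single model, and states the aim: "we seek a sample size that gives us sufficient power to detect both the main effect of intervention and important interaction effects". It then turns to effects of the interventions, in the plural, on other outcomes. "For the continuous outcomes, we used block person-randomized trial module in Optimal Design". The inputs are 24 physicians as blocks, about 9 patients each, α of .05, "between-physicians variability in effect size (σ_{β}^2) of .05", and "5% of variance in outcomes due to physicians and a medium effect size (d) of .50, power to find effects exceeds .90". No separate figure is given for the physician intervention.

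Under Models for Aim 1, Hypothesis 1b is judged by the significance of a 0/1 variable for whether the physician had been trained at the time of the visit. The same model carries the booklet indicator and the product of the two. Because this part of the design is quasi-experimental, Control variables adds that "we will also control factors that might threaten the internal validity of the intervention, such as time since study has begun". The functional form of time is not given.

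On timing, Study Design Overview says that "physicians provide pre-intervention data for 20 months, then receive the intervention and continue their participation for another 20 months". The project summary places a 2-month intervention period between the two blocks, and half of the patients take part on each side.

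**The concern.** A block-randomised power calculation treats the intervention as unrelated to any covariate. Randomisation within physician secures this for the booklet. The physician intervention is not randomised: it switches from 0 to 1 once, in mid-study, so it rises with calendar time by construction. Once time is in the model, only the part of the indicator that time does not explain carries information on H1b, and the standard error grows. The power section makes no allowance for this.

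H1b is one of the two main-effect hypotheses, and support for it is defined by significance alone. Beside a stated power above .90, a non-significant result invites the conclusion that the training does not work, when a true medium effect would more likely than not have been missed.

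**Working it through.** **Inputs from the protocol.** J = 24 physicians, n = 9 patients each, α = .05 (taken as two-sided), d = .50, effect variance between physicians .05, pre and post halves equal, phases at months 0–20 and 22–42.

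**Assumptions not in the documents.** Linear time; visits evenly spread within each phase; residual variance 1.

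**1. The stated figure.** λ = J·d² / (.05 + 4/n) = 24 × .25 / (.05 + .444) = 6/.494 = 12.1. With F(1, 23), power is .915, which agrees with the protocol.

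**2. Correlation of the indicator with time.** The phase midpoints are months 10 and 32, so the between-phase variance of time is 11² = 121. The within-phase variance is 20²/12 = 33.3. Then r² = 121/154.3 = .784, r = .885, and the variance inflation is 1/(1 − .784) = 4.63.

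**3. H1b with time in the model.** Only the sampling term is inflated: λ = 6 / (.05 + .444 × 4.63) = 6/2.108 = 2.85, power .37. The standard error goes from √(.494/24) = .144 to √(2.108/24) = .296. A generalised least squares check with random physician intercepts and effects also gave .365.

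**4. Adding the planned product term.** With 0/1 coding, the pre/post coefficient becomes the effect in usual-care patients only, and the factor rises to 4.63 + 1 = 5.63: λ = 6/2.552 = 2.35, power .31.

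**5. Detectable effect at 80% power.** This needs λ of about 8.56, so d = √(8.56 × variance term / 24).
- No time term: √(8.56 × .494/24) = .42.
- With time: √(8.56 × 2.108/24) = .87.

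**6. Other visit patterns (linear time throughout).**

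| Pattern | Inflation | Power | Power with product term |
|---|---|---|---|
| Bunched at the ends of each phase | 3.42 | .47 | .38 |
| Pre visits late, post visits early | 3.65 | .44 | .36 |
| Even | 4.63 | .37 | .31 |
| Front-loaded in both phases | 6.45 | .28 | .25 |
| Only the first 10 months of each phase | 15.5 | .14 | .14 |

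Even visits with physician starts staggered over 6 or 12 months give .38 or .42 (.32 or .35 with the product term).

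**7. Inflation that could be tolerated.** Power of .80 needs a factor of 1.46 or less, and .90 needs 1.07 or less.

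**8. Credit for other covariates.** If they explain 10% to 40% of the residual variance (assumed), the even-visit figure becomes .40 to .54; at 40%, λ = 6/(.05 + .444 × 4.63 × .6) = 6/1.285 = 4.67. Combining 40% with the most favourable pattern gives λ = 6/(.05 + .444 × 3.42 × .6) = 6/.962 = 6.24, power about .67, still short of .80.

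**The case against.** **Scope.** The power section ties its first calculation to patients randomised to the booklet and names a person-randomised module, so the figure may have been meant for H1a only. But the sentence introducing the continuous outcomes speaks of the interventions in the plural, and no other figure is offered for H1b. On the narrowest reading, H1b has no stated power at all.

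**Assumptions.** Linear time and even visits are not in the documents, and .37 is not a ceiling: step 6 reaches .47. Staggered starts are plausible, since each site begins after its own approval. Credit for other covariates is fair too, and the unit of analysis is described as the visit, so there may be more than 9 observations per physician. All of this stands and is why a range is needed. No case calculated reaches .80. In the other direction, the number of boosters received is also a listed control. Physician Intervention describes the post-training reminder card as a booster, so on that reading the variable is zero throughout the pre phase and adds collinearity not counted here.

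**Stronger readings to avoid.**
- A reader might infer that time and the indicator are effectively one variable. At r = .885, about 22% of the indicator's variance is independent of time; the effect can be estimated, though imprecisely.
- A reader might take the plan to recruit patients promptly in each phase as placing the visits early. The documents do not say this: recruited patients are tracked until potentially eligible, and may then have up to four visits. The 10-month row is a hypothetical.
- A reader might conclude that the time term should go. It is there to guard a quasi-experimental comparison against trend; dropping it would regain power by leaving that trend uncontrolled.

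**Conclusion.** The point holds as a mismatch between the power calculation and the model, not as an arithmetic error: the stated figure is right for the calculation that was run. It describes the randomised booklet contrast and does not carry over to H1b. Under linear time and even visits, H1b power at d = .50 is about .37, or about .31 with the product term. Across the visit patterns tried it is roughly .14 to .47 before any credit for covariates, and about .54 for even visits if covariates explain 40% of residual variance. The exact value depends on visit dates and on the form of the time term, neither of which the documents give. The conclusion that power is far below .90 does not depend on them within the range tried.

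The same collinearity affects H1b for the primary binary outcome, but these figures are for continuous outcomes and should not be transferred to it. The randomised comparison is not affected by the time term, because randomisation runs within both phases.

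**What to change.** - In Power and Sample Size Estimates, limit the statement of power above .90 to the booklet contrast (H1a), and say that it refers to the booklet effect averaged over the two phases.
- Add H1b power and detectable effect, for the continuous outcomes and for the primary binary outcome, calculated under the model to be fitted with both the time term and the product term. Give a range over stated visit-timing assumptions, not one number, and state the functional form of time.
- Keep the time term.
- Under Hypothesis 1b, state that the result is the time-adjusted estimate with its confidence interval, and that a non-significant coefficient will not be read as evidence of no effect.

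The cost is one recalculation, some protocol wording and a less favourable stated figure. No extra patients or changes to study procedures are needed.

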Time 2: Pre- and Post-Clinic Visit: On the day of a clinic visit (for those patients who have been prescreened and found to be potentially eligible for an available clinical trial), clinic/research staff will meet with patients to remind them that the visit will be video recorded and to provide a copy of the patient intervention booklet, if needed. Just prior to and following the visit, patients will complete brief questionnaires (See Appendices H and I: Time 2 pre- and post questionnaires). If family members or companions are present, they will be told about the study and asked for consent (See Appendix C: Companion Information Sheet). Similarly, clinical staff who will be in the room during video recording will be provided an information sheet (See Appendix D: Health Care Provider Information Sheet.) Patients will receive a \$10.00 gift card following this visit. Also, patients will be asked whether they were offered a clinical trial; if they were not, they will be told that they are still in the study and may be contacted again in the future. They will continue to be tracked for up to a total of 4 visits or until the end of their participation. If they still receive no offer after a fourth visit, they will no longer be tracked. If they are offered a trial, they will proceed to Time 3.

Time 3: Follow-Up Interview: A week after the visit, research staff will contact patients (on the phone or in person as convenient to patients) who were offered a trial to conduct a brief interview (Appendix J: Time 3 Follow-Up Interview). This interview should take approximately 20 minutes. Patients will receive a third \$10.00 gift card at the end of this interview.

Time 4: Medical Record Review: Research staff will examine patient medical records to determine participating patients' disease status, co-morbidities, whether and when they were eligible for an available trial, whether they completed procedures for trial enrollment and/or enrolled in a trial, and trial characteristics (e.g., difficulty, complexity) that may affect physicians' decisions to offer a trial and/or patients' decisions to participate.

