We will use Multi-Level Models (MLMs) that include separate variables identifying both interventions, as well as a variable indicating the interaction between the two phases. This model allows us to examine the main effect of each intervention, and multiplicative effects of having been exposed to both interventions. For purposes of clarity, we discuss hypotheses for each intervention separately, but as already noted, they will be tested in the same MLMs. We will model most outcomes (specifically, patients' perceptions of patient-centeredness, perceived involvement in care, trust in physician, and team perceptions; patient active participation, and physician patient centeredness, patient understanding of informed consent) as continuous variables. We will use binomial logistic models for binary outcomes (e.g., trial offer) and multinomial logistic regression for categorical outcomes (e.g., patients' self-reported participation decision - "yes", "no", "undecided"). We will also explore whether a single model best captures the meditational processes for both Black and White patients or separate models are needed.

Models for Aim 1: As we have described the objectives and outcomes above, here we generally describe the models that will be used to test support for our hypotheses. All outcomes, and coefficients for each of the intervention effects and interactions between them, will be modeled at the patient level of the model (level-1); that is, they will be nested within physicians (level-2). We will use one MLM for each outcome to test the three Aim 1 hypotheses. We use this particular approach to examine the interventions' effects because it is believed that the two interventions will not only work independently, but also interactively. Thus, we use a model that simultaneously controls for the main and interactive effects of both interventions as we examine their unique contributions.

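### The Aim 1 models adjust for a count of previous patient-physician interactions with no cut-off at randomisation, so the randomised comparison can end up adjusted for something treatment changes

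*Combined protocol and SAP*

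**What the plan says.** The Control variables paragraph of the Statistical Analyses gives the reason for this group of covariates: "Because the physician-focused phase involves a quasi-experimental design, we will also control factors that might threaten the internal validity of the intervention". It then names them: "such as time since study has begun, and number of previous interactions between patients and physicians". It gives no start or end point for counting interactions.

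The reason given concerns the physician pre/post comparison, but the covariate is not confined to it. Under Models for Aim 1 the plan states: "We will use one MLM for each outcome to test the three Aim 1 hypotheses". The same adjusted model therefore tests the patient intervention (H1a), the physician intervention (H1b) and their interaction (H1c).

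Two other sections determine what the count could contain. In the Study Design Overview, patients are "tracked until they become eligible for a trial, at which time they will be randomized into an intervention or usual care group", and they then continue until "they receive a trial offer, or they have four interactions with their physician without receiving an offer". Time 2 repeats the limit: "They will continue to be tracked for up to a total of 4 visits or until the end of their participation", and "If they still receive no offer after a fourth visit, they will no longer be tracked".

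**The concern.** The Study Design Overview uses the word interactions for the visits that follow randomisation, and their number depends on when an offer is made. A man offered a trial at his first study visit has no earlier study visit. A man never offered one can run to the limit of four. If the booklet or the physician training brings offers forward, it lowers the count.

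An offer comes before the enrolment decision and is itself a secondary outcome. In a patient-level model, a count that includes post-randomisation visits therefore partly stands in for the offer. Adjusting for it conditions on a consequence of treatment. For H1a, that gives up the protection randomisation would otherwise provide. For H1b, the same stopping rule acts on patients seen after the physician training.

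The primary outcome is at stake. Two analysts following the same text could count differently and report different treatment coefficients.

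**Working it through.** **Inputs from the documents.** At most four interactions after randomisation, ending at an offer (Study Design Overview; Time 2). Planning rates of 25% and 35% for a decision to enrol (Power and Sample Size Estimates).

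**Assumed, because the documents do not give them.** Offer rates, acceptance rates, the number of interactions before randomisation (Poisson with mean 0, 2 or 5), 1:1 allocation and a constant chance of an offer at each visit. Men never offered a trial count as not enrolling. Clustering by physician is left out. The adjusted figures are large-sample logistic fits to this process.

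**The plan's own effect size.** Odds are 0.25/0.75 = 0.333 and 0.35/0.65 = 0.538. The odds ratio is 0.538/0.333 = 1.615 and its log is 0.480, which agrees with the plan's b = 0.48. The power the plan attaches to this effect is a separate matter and is not used here.

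**Case 1: offers 20% versus 30% per visit, 45% accepted in both arms.**
- Offered by visit four: 1 − 0.8⁴ = 0.590 and 1 − 0.7⁴ = 0.760.
- Deciding to enrol: 0.590 × 0.45 = 0.266 and 0.760 × 0.45 = 0.342.
- Odds ratio: (0.342/0.658)/(0.266/0.734) = 1.44, log 0.362.
- Mean study visits: 1 + 0.8 + 0.64 + 0.512 = 2.95 and 1 + 0.7 + 0.49 + 0.343 = 2.53. Treatment changes the count.
- One row per patient, adjusted for post-randomisation visits only: log odds ratio 0.149 (odds ratio 1.16). Loss 1 − 0.149/0.362 = 59%.
- With a mean of 2 earlier visits in the count: 0.270, loss 25%. With a mean of 5: 0.314, loss 13%.
- Simulations at the same rates gave about 58%, 25–26% and 13%, so the two approaches agree.
- Adjusted for pre-randomisation visits only: 0.362, no loss.
- Visit-level model with the count as a visit index: 0.456 with and without adjustment.

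**Case 2: rates set to reproduce the plan's 25% versus 35%.** The unadjusted patient-level log odds ratio is 0.480 in every row. Cells give the adjusted value.

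| Effect runs through | Post-randomisation visits only | plus mean 2 earlier | plus mean 5 earlier |
|---|---|---|---|
| Offers only (0.50 to 0.70 overall, acceptance 0.50) | 0.211 (56% lost) | 0.367 (24% lost) | 0.422 (12% lost) |
| Both (offers and acceptance each 0.50 to 0.592) | 0.405 (15% lost) | 0.447 (7% lost) | 0.463 (3% lost) |
| Acceptance only (0.417 to 0.583, offers 0.60) | 0.565 (18% larger) | 0.513 (7% larger) | 0.497 (4% larger) |

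Counting only pre-randomisation interactions leaves 0.480 in all three rows. In a visit-level model, the enrolment coefficient is the same with and without the count in all three (0.547, 0.443 and 0.374).

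**Restricting the analysis.** Among offered patients only, the count changes nothing. For acceptance rising from 45% to 60% the log odds ratio is 0.606 both ways. For visits in which a trial was discussed, the loss ranged from nil to about 13%.

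**The case against.** The strongest reply is that the plan never says post-randomisation visits are counted. Earlier interactions certainly exist: the inclusion criteria admit men who have been seeing the physician for up to a year, and recruited men are tracked through further visits until a trial is available. The stated purpose, protecting the pre/post physician comparison, fits a measure of how established the relationship was at baseline. This stands as far as it goes. A baseline count is compatible with the text, and a reader who infers that the protocol definitely counts the study visits goes beyond it. The text does not secure the baseline reading either. It sets no cut-off, and it uses the same word for the visits after randomisation.

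The second reply is that the analysis may be at visit level, where the count does little or no harm. The power section calls the visit the unit of analysis, and Hypothesis 1a refers to visits in which a trial was discussed. That would remove most of the problem. But the power section also defines success per patient and counts 216 patients, and Models for Aim 1 places all outcomes at the patient level. The unit is unsettled, and an enrolment decision most naturally has one row per patient.

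The third reply is that a large loss needs several conditions together: one row per patient, a count made up mainly of post-randomisation visits, an effect that runs through offers, and never-offered men analysed as failures. This stands. The booklet also aims at teamwork and question-asking, so an effect through acceptance is plausible, and there the coefficient moves the other way.

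**Conclusion.** The concern holds in a conditional form. The covariate has no cut-off at randomisation, it sits in the model that tests the randomised contrast, and the stopping rule lets treatment change a count taken at the outcome visit. In a patient-level model of the enrolment decision, it can distort the H1a and H1b coefficients.

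The size depends on assumptions the documents do not settle. When the effect runs through offers, the loss is a little over half of the log odds ratio if only post-randomisation visits are counted (58–59% in case 1, 56% in case 2). It falls to roughly 12% to 26% once a mean of 5 or 2 earlier visits is included. If the effect runs only through acceptance, the coefficient is inflated by 4% to 18% in case 2. In a visit-level model with a constant chance of an offer, there is little or no change.

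A reader might infer that the adjustment removes most of the effect, or that it always biases toward no effect. The documents support neither: they give no offer or acceptance rates, and the direction depends on the pathway. What they do support is that the plan leaves open an adjustment for a post-randomisation variable in its randomised comparison.

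**What to change.** For patient-level outcomes, define the covariate as the number of interactions with the participating physician up to the Time 1 randomisation, and state that these models will not adjust for the number of visits after it. In any visit-level model, use study-visit number only as a time index.

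This does more than supply a missing definition. It replaces a covariate that treatment can change with a baseline one, and still lets the physician comparison adjust for how established the relationship was.

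The cost is one phrase in Control variables. Staff already track scheduled visits from recruitment, and medical records are already reviewed at Time 4, so the baseline count should need no new data collection.
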